1. ABBREVIATIONS AND DEFINITIONS

AE Adverse Event

AR Adverse Reaction
CRF Case Report Form

CRO Contract Research Organization

EC Ethics Committee

GCP Good Clinical Practice

h Hour

HADS Hospital Anxiety and Depression Scale

ICH International Committee for Harmonization

IEC Independent Ethics Committee

incl. including mL Milliliter

NA Not Applicable

NIHSS National Institute of Health Stroke Scale

SAE Serious Adverse Event

SAR Serious Adverse Reaction

SUSAR Suspected Unexpected Serious Adverse Reaction

VCI Vascular Cognitive Impairment

WAIS Wechsler Adult Intelligence Scale

2. PROTOCOL SUMMARY / SYNOPSIS

Title	Combined Neuropsychological, Neurophysiological and	
TIGG		
	Psychophysiological Assessment of the Effects of N-Pep-	
	12 on Neurorecovery in Patients After Ischemic Stroke –	
	N-PEP-12 EXTENSION	
Name of product	MemoProve / Cebrium	
Name of active substance	N-PEP-12	
Phase	Phase IV	
Indication	Ischemic Stroke	
Study Design	Exploratory, prospective, randomized, open label, controlled study	
Number of sites & countries	1 center Romania	
Sample Size	Stroke Group – minimum 90 patients	
	Intervention Group: N = 60	
	Reference Group: N = 30	
Primary Objectives	To assess the efficacy of 360 days of once-daily diet supplementation with 90 mg N-Pep-12 on the neurocognitive function and neurorecovery outcome in patients with post-stroke cognitive impairment.	
Secondary Objectives	 To assess the safety of 360 days of once-daily diet supplementation with 90 mg N-Pep-12 on the neurocognitive function and neurorecovery outcome in patients with post-stroke cognitive impairment. To assess study group baseline differences between N-PEP-12 treated patients and controls using quantitative electroencephalography (QEEG) and eye tracking (ET) at day 360, in patients with available recordings (subgroup 	

Combined Neuropsychological, Neurophysiological and Psychophysiological Assessment of the Effects of N-Pep-12 on Neurorecovery in Patients after Ischemic Stroke

	analysis).	
Primary Variable	Stroke Group	
	Montreal Cognitive Assessment (MoCA)	
	 Hospital Anxiety and Depression Scale (HADS) 	
	Digit Span (DS)	
	Color Trial Test (CTT)	
	Processing Speed Index (PSI)	
Secondary Variables	AE, SAE Date/time	
	Deletionalia (Oesianos es /Oesta	
	o Relationship/Seriousness/Outco	
	Mortality:	
	Date/time	
	o Cause	
	Subgroup analysis	
	 QEEG parameters 	
	 Eye tracking parameters 	
Inclusion Criteria	Stroke onset – 30-120 days prior to screening	
	Stroke is ischemic in origin, supratentorial, and radiologically confirmed (CT or MRI)	
	No significant pre-stroke disability (pre-stroke Modified Rankin Score of 0 or 1)	
	Goodglass and Kaplan Communication Scale	
	Score of > 2 at screening	
	No other radiologically confirmed stroke in the	
	3 months preceding index stroke	
	Age between 18 and 80 years, inclusive	
	Signed informed consent form	

Combined Neuropsychological, Neurophysiological and Psychophysiological Assessment of the Effects of N-Pep-12 on Neurorecovery in Patients after Ischemic Stroke

Fuelveien Oritorie		
Exclusion Criteria	Pre-existing and active major neurological disease	
	 Pre-existing and active (e.g., on chronic medication) major psychiatric disease, such as major depression, schizophrenia, bipolar disease, or dementia (the short Informant Questionnaire on Cognitive Decline in the Elderly (IQCODE) score >3) 	
	Advanced liver, kidney, cardiac, or pulmonary disease	
	A terminal medical diagnosis consistent with survival < 1 year	
	Major drug dependency, including alcohol (in the investigator's judgment).	
	 Injury of writing hand influencing cognitive or other outcome measures, in the investigator's judgment. 	
	Females who are pregnant or lactating.	
Visit Schedule	Visit 1 – Screening / Baseline	
	Day – Baseline - 30-120 days from stroke onset	
	Visit 2 – Efficacy / Safety	
	Day – 90 days from baseline	
	Visit 3 – Efficacy / Safety	
	Day – 360 days from baseline	
Documented parameters	Visit 1 – 30-120 days from stroke onset	
	Patient logistics	
	Patient demographic data (age, gender, ethnicity)	
	Patient medical history and risk factors	
	Patient medical history and risk factors	
	 Patient medical history and risk factors Inclusion/exclusion criteria 	

	QEEG/ET parameters	
	Visit 2 – 90 days from baseline	
	o Patient logistics	
	 All primary efficacy assessment scales 	
	o QEEG/ET parameters	
	Visit 3 – 360 days from baseline	
	o Patient logistics	
	 All primary efficacy assessment scales 	
	 QEEG/ET parameters 	
Statistical methods	The statistical analyses in this study will be exploratory in	
	nature because the study is not powered to address any	
	pre-defined statements but to generate valid hypotheses	
	on efficacy and safety issues for future studies. A formal	
	sample size calculation for confirmatory trials was not	
	performed.	

3. INTRODUCTION

3.1. Background information

Cognitive impairment is a common finding in patients with stroke, regardless of severity, and it has an important impact on quality of life. Vascular cognitive impairment (VCI) describes a spectrum of cognitive disorders ranging from mild cognitive impairment (MCI) to dementia, with consequences for all cognitive domains and behavior (Jellinger K. A., 2013). However, there is increasing evidence to suggest the disproportionate impairment of executive function, including working memory, abstraction, reasoning, verbal fluency, and cognitive flexibility (Sachdev P.S. et al, 2004; Sörös P. et al., 2015). In epidemiological studies of stroke, cognitive impairment ranges from 20% to 80%; this variation depends on several factors, especially the diagnostic criteria (Sun J.H. et al., 2014). For example, the prevalence of the cognitive impairment 3 months after stroke can present a variation up to 72% depending on the complexity of the neuropsychological assessment (Gutiérrez P.C. et al., 2011; Douiri A., et al, 2013).

This is a pilot study to investigate the effects of N-Pep-12 diet supplementation on the neurorecovery of patients with post-stroke cognitive impairment. N-Pep-12 is a proprietary, peptide-based nutritional supplement that has been shown to exert neuroprotective and procognitive effects in experimental studies (Hutter-Paier B. et al., 2015) as well as in earlier

clinical studies in patients suffering from age-related cognitive deficits (Alvarez X.A. et al., 2005; Crook T.H. et al., 2005). Remarkably, N-Pep-12 has been shown to significantly improve memory impairment in older adults with subjective memory complaints after only 30 days of a once-daily intervention with 90 mg of the compound (Crook T. H. et al., 2005). The compound is available in the form of film-coated tablets or capsules under the brand names Memoprove and Cebrium. Furthermore, qEEG power analysis showed that N-Pep-12 is able to improve vigilance after only a single dose (Alvarez X.A. et al., 2005).

This study will use a multidimensional approach that will combine neuropsychological outcome scales, neurophysiological investigations (qEEG), psychophysiological investigations (eye-tracking), and clinical parameters.

Eye tracking involves looking at targets on a computer screen while a special system records eye movements and changes in pupil diameter in response to the movements of the targets. Patterns of eye movements offer information about what a person is processing at a particular moment and the time course of processing visual information. Smooth pursuit and saccades are the two components of tracking eye movements. Smooth pursuit, or just pursuit, is a class of slow eye movements that minimizes retinal target motion. Saccades are rapid eye movements that align the fovea with the target. Their coordination is usually studied by investigating the latencies of pursuit onset in response to a moving target appearing simultaneously with the disappearance of the stationary fixation target. Because the saccades and fixations recruit the same neuroanatomical circuitries as attention, involving the dorsolateral prefrontal cortex, and also because eye movements can be influenced by emotions, it has been suggested that eye tracking can be used as a biomarker for cognitive dysfunction (Munoz D.P., 2002; Seligman S. C. and Giovannetti T., 2015).

Due to its highly accurate temporal resolution, the qEEG technique (with 19 channels) provides a unique window to assess the brain dynamics underlying cognitive functions. qEEG has been used for the evaluation of Alzheimer's disease (Chen C.C. et al., 2013), vascular dementia (Neto E. et al, 2015), and Parkinson's disease-associated dementia (Caviness J.N. et al., 2015). It also can reveal abnormalities in the preclinical stages of cognitive impairment (When D. et al., 2015). Typical EEG findings in patients with Alzheimer's disease (AD) include increased slow wave and decreased fast wave activities. (Alvarez X. A. et al., 2000; Alvarez X.A. et al., 2003; Alvarez X. A. et al., 2008).

4. STUDY OBJECTIVES

The study shall assess the therapeutic effect and the safety of a single daily dose of 90 mg of N-Pep-12 in supporting neurorecovery in comparison to a control group of patients after stroke. This is an exploratory study, and the dosage, route of administration and intervention duration were chosen according the current instructions for use provided by the manufacturer of N-Pep-12. The study aims to show the superiority of N-Pep-12 over the control group in the neurorecovery outcome after 360 days.

4.1. Primary Objective

To assess the efficacy of 360 days of once-daily intervention duration with 90 mg N-Pep-12 on neurocognitive function and neurorecovery outcome in patients with post-stroke cognitive impairment.

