7. SELECTION AND WITHDRAWAL OF PATIENTS

7.1. Patient Inclusion Criteria

- Stroke onset 30-120 days prior to screening
- Stroke is ischemic in origin, supratentorial, and radiologically confirmed (CT or MRI)
- No significant pre-stroke disability (pre-stroke Modified Rankin Score of 0 or 1)
- Goodglass and Kaplan Communication Scale Score of > 2 at screening
- No other radiologically confirmed stroke in the 3 months preceding index stroke
- Age between 18 and 80 years, inclusive.
- Signed informed consent form

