7.2. Patient Exclusion Criteria

- Pre-existing and active major neurological disease
- Pre-existing and active (e.g., on chronic medication) major psychiatric disease, such as major depression, schizophrenia, bipolar disease, or dementia (the short Informant Questionnaire on Cognitive Decline in the Elderly (IQCODE) score >3)
- Advanced liver, kidney, cardiac, or pulmonary disease
- A terminal medical diagnosis consistent with survival < 1 year
- Major drug dependency, including alcohol (in the investigator's judgment).
- Injury of writing hand influencing cognitive or other outcome measures, in the investigator's judgment.
- Females who are pregnant or lactating.

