10.1. Primary Variables

MoCA

Montreal Cognitive Assessment (MoCA) was designed as a rapid screening instrument for mild cognitive dysfunction. It assesses different cognitive domains: attention and concentration, executive functions, memory, language, visuo-constructional skills, conceptual thinking, calculations, and orientation. The time to administer the MoCA is approximately 10 minutes. The total possible score is 30 points; a score of 26 or above is considered normal.

• Processing Speed Index, Wechsler Adult Intelligence Scale, Fourth Edition

The Processing Speed Index (PSI) assesses skills such as focusing attention and quick scanning as well as discriminating between and sequentially ordering visual information. It requires persistence and planning ability, but it is sensitive to motivation, difficulty working under time pressure, and motor coordination as well. It is also related to reading, mathematical, and memory skills. Cultural factors seem to have little impact on processing speed. Processing Speed (PS) refers to the speed at which cognitive processes can be performed.

• Digit Span, Wechsler Adult Intelligence Scale, Fourth Edition

The Digit Span task exercises a patient's verbal working memory. Attention and comprehension also contribute to performance. The digit span task is a common component of many IQ tests, including the widely used WAIS (Wechsler Adult Intelligence Scales).

Performance on the digit span task is also closely linked to language learning abilities. The procedures for this assessment of working memory are considered standard. A list of numbers is read out loud at a rate of one number per second, and the participant is then asked to recall the numbers in order. The first list consists of three numbers and increases until the person begins to make errors. Lists with recognizable patterns (e.g., 1, 3, 5, 7, and 9) should be avoided, as people may remember these numbers more easily. At the end of each sequence, the participant is asked to the recall items in order. The average adult can remember a sequence of seven numbers, plus or minus two. This test can be distributed both backwards and forwards. Scores are thought to correlate with age and not intelligence.

Hospital Anxiety and Depression Scale

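### The efficacy and safety objectives name patients with post-stroke cognitive impairment, but no entry criterion requires impairment, so the whole-sample comparison describes ischaemic stroke patients generally

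*Protocol*

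**What the plan says.** The synopsis and section 4.1 set the efficacy objective in terms of "neurocognitive function and neurorecovery outcome in patients with post-stroke cognitive impairment". Section 4.2 and the synopsis use the same population for the safety objective, and section 3.1 describes the pilot in the same terms.

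Other parts name a wider population. The general statement in section 4 plans to assess the product "in comparison to a control group of patients after stroke", without mention of impairment. The synopsis gives the indication as ischaemic stroke, and the study title refers to patients after ischaemic stroke.

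Eligibility follows the wider population. Section 7.1 asks for:

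- timing: "Stroke onset 30-120 days prior to screening"
- type: "Stroke is ischemic in origin, supratentorial, and radiologically confirmed (CT or MRI"
- a pre-stroke modified Rankin score of 0 or 1
- communication: "Goodglass and Kaplan Communication Scale Score of > 2 at screening"
- no other confirmed stroke in the 3 months before the index stroke
- age 18 to 80
- signed consent

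The one criterion in section 7.2 with a cognitive measure excludes pre-existing "dementia (the short Informant Questionnaire on Cognitive Decline in the Elderly (IQCODE) score >3".

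Section 10.1 gives MoCA a maximum of 30 and says that "a score of 26 or above is considered normal", but no cut-off is applied at entry. Under section 12.1, eligibility is confirmed, the randomisation code is assigned, and the baseline efficacy tests come afterwards.

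**The concern.** The two objectives ask about one population and the entry criteria deliver another. None of the seven inclusion criteria requires a deficit, and the cognitive exclusion removes patients rather than selecting impaired ones. Because the baseline tests follow randomisation, MoCA cannot act as an entry screen as the visit is written.

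If the plan is followed, a difference (or no difference) found in a mixed stroke population would be reported as a finding about patients with post-stroke cognitive impairment. If the product acts mainly in impaired patients, unimpaired entrants would also dilute the whole-sample effect. On MoCA, a patient who starts at 26 to 30 has between 4 and 0 points left to gain.

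**Working it through.** **Step 1: does anything require impairment?** The synopsis criteria match sections 7.1 and 7.2. Stroke timing, type, recurrence, age and consent say nothing about cognition. The pre-stroke Rankin and communication thresholds are limits on disability and on language difficulty, so they tend to select better-preserved patients. The IQCODE criterion concerns decline before the stroke; it neither excludes impairment due to the index stroke nor requires it. Section 12.1 adds no later filter. The only subgroup analyses the protocol names are QEEG and eye tracking (sections 4.2.1 and 10.2).

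**Step 2: how many patients might be affected?** The protocol gives no figure for its own population. Its only figure is in section 3.1: "In epidemiological studies of stroke, cognitive impairment ranges from 20% to 80" per cent, with the variation attributed especially to diagnostic criteria. Taken purely as a range, it gives for 90 randomised patients:

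- impaired: 0.20 × 90 = 18 to 0.80 × 90 = 72
- not impaired: 90 − 72 = 18 to 90 − 18 = 72
- impaired by arm at 2:1: 12 versus 6, up to 48 versus 24

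**Step 3: what could dilution cost?** There is no sample-size figure to reproduce, because the synopsis says no formal calculation was done.

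From the protocol: 60 versus 30 patients, and the range in step 2. Assumed, not in the protocol: two-sided 5% test, unit SD, an effect of 0.6 SD in impaired patients and none in the others, no dropout.

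*Whole sample.* SE = √(1/60 + 1/30) = 0.2236. With impaired share f, the average effect is 0.6f and power ≈ Φ(0.6f/0.2236 − 1.96).

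*Impaired patients only.* SE = √(1/(60f) + 1/(30f)) and power ≈ Φ(0.6/SE − 1.96).

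| Impaired share f | Average effect (SD) | Whole-sample power | Impaired only, n | SE | Impaired-only power |
|---|---|---|---|---|---|
| 1.0 | 0.60 | Φ(2.683 − 1.96) = 0.765 | 60 vs 30 | 0.2236 | 0.765 |
| 0.8 | 0.48 | Φ(2.147 − 1.96) = 0.57 | 48 vs 24 | 0.2500 | Φ(2.400 − 1.96) = 0.67 |
| 0.5 | 0.30 | Φ(1.342 − 1.96) = 0.27 | 30 vs 15 | 0.3162 | Φ(1.897 − 1.96) = 0.475 |
| 0.2 | 0.12 | Φ(0.537 − 1.96) = 0.08 | 12 vs 6 | 0.5000 | Φ(1.200 − 1.96) = 0.22 |

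The pattern is the same for other assumed effects. At 0.5 SD, whole-sample power goes from 61% (all impaired) to 43% (80% impaired) and 6% (20% impaired). At 0.8 SD it goes from 95% to 82% and 11%.

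**Step 4: what would an entry criterion cost?** To randomise 90 impaired patients, the number of otherwise eligible patients screened is 90/f: 90/0.8 = 112.5, so 113, up to 90/0.2 = 450. Section 7.3.1 stops the study if under 30% of the sample, 0.30 × 90 = 27 patients, is recruited in one year.

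**The case against.** **The study is exploratory and states that it is not powered for pre-defined statements.** This stands against any argument from power, so the power figures serve only to illustrate. It does not remove the mismatch, since a hypothesis-generating study still has to be about the population it names.

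**Baseline MoCA is recorded, so impaired patients can be analysed separately, and an SAP that is not shown may provide for this.** This also stands in part. A reader might infer that the impairment question cannot be answered at all. The documents do not support that; it is the whole-sample comparison that does not answer it. But an SAP cannot change who is randomised or reconcile the protocol's own objectives with its criteria.

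**Normal patients are not necessarily at a ceiling.** A reader might infer that cognitively normal patients cannot show recovery on the primary endpoints. That is unsupported. The documents show limited headroom only for MoCA, one of five primary endpoints, and even there up to 4 points remain. No ceiling is stated for CTT, DS or PSI, and HADS measures anxiety and depression. MoCA is also described as a screening tool, so a score of 26 or above need not exclude every deficit, and arms can differ through less decline.

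**The 20% to 80% range is not the trial's prevalence.** Correct. It is a spread across diagnostic criteria, not the share with MoCA below 26 at 30 to 120 days. It would be wrong to say that 20% to 80% of those randomised will fall outside the stated population.

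**The dementia exclusion fits an objective about post-stroke impairment.** Also correct, since it concerns pre-existing disease. It is not a fault in itself; it simply does not select impaired patients.

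**Conclusion.** The mismatch holds on the text alone. The efficacy and safety objectives name patients with post-stroke cognitive impairment; eligibility, the general statement in section 4 and the synopsis indication describe ischaemic stroke patients generally. Cognitively normal patients can be randomised, and the whole-sample day-360 result applies to the wider group.

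The size is uncertain because the share of unimpaired entrants is unknown. If a 0.6 SD effect were confined to impaired patients, whole-sample power would fall from about 76% to 57%, 27% or 8% with 80%, 50% or 20% impaired. Restricting to impaired patients recovers part of the loss (about 67%, 47% or 22%). These figures rest on the assumed effect, the 5% level and no effect in unimpaired patients; the mismatch does not.

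Because the study is exploratory and rewording can close the gap without changing enrolment, this is a should-fix rather than a must-fix.

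**What to change.** Preferred change, usable whether or not enrolment has begun:

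- In the synopsis and sections 4.1 and 4.2, restate the efficacy and safety objectives for patients after ischaemic stroke, in line with section 4 and the indication.
- Name the day-360 comparison in patients with baseline MoCA below 26, the protocol's own limit of normal, as the analysis that addresses the impairment question.
- In section 12.1, take MoCA before randomisation. The study is open label, so the score that defines this group should be fixed before the arm is known.

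The cost is an amendment to wording and visit order, and a smaller N for the impaired-patient analysis (12 versus 6 to 48 versus 24 on the section 3.1 range). For patients already randomised, MoCA will have followed allocation, which should be reported.

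Alternative, only if enrolment has not begun and slower accrual is acceptable: add MoCA below 26 at screening to the synopsis and section 7.1, and change the order in section 12.1 so that the test precedes randomisation. All 90 patients would then belong to the population of the objectives. About 113 to 450 otherwise eligible patients would have to be screened at this single centre, which must be weighed against the recruitment stopping rule in section 7.3.1.

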4.1.1. Primary End-Points

- o MoCA
- HADS
- o CTT
- o DS
- o PSI

4.2. Secondary Objective

To assess the safety of 360 days of once-daily intervention duration with 90 mg N-Pep-12 on neurocognitive function and neurorecovery outcome in patients with post-stroke cognitive impairment.

4.2.1. Secondary End-Points

- Safety variables.
- Subgroup analysis
 - QEEG parameters
 - Eye tracking parameters

5. STUDY DESIGN

Exploratory, prospective, randomized, open label, controlled study.

6. STUDY CENTER

"RoNeuro" Institute for Neurological Research and Diagnostic, Cluj-Napoca, Romania.

7. SELECTION AND WITHDRAWAL OF PATIENTS

7.1. Patient Inclusion Criteria

- Stroke onset 30-120 days prior to screening
- Stroke is ischemic in origin, supratentorial, and radiologically confirmed (CT or MRI)
- No significant pre-stroke disability (pre-stroke Modified Rankin Score of 0 or 1)
- Goodglass and Kaplan Communication Scale Score of > 2 at screening
- No other radiologically confirmed stroke in the 3 months preceding index stroke
- Age between 18 and 80 years, inclusive.
- Signed informed consent form

7.2. Patient Exclusion Criteria

- Pre-existing and active major neurological disease
- Pre-existing and active (e.g., on chronic medication) major psychiatric disease, such as major depression, schizophrenia, bipolar disease, or dementia (the short Informant Questionnaire on Cognitive Decline in the Elderly (IQCODE) score >3)
- Advanced liver, kidney, cardiac, or pulmonary disease
- A terminal medical diagnosis consistent with survival < 1 year
- Major drug dependency, including alcohol (in the investigator's judgment).
- Injury of writing hand influencing cognitive or other outcome measures, in the investigator's judgment.
- Females who are pregnant or lactating.

